### **3.1.3 Sample size**

The main sample size consideration is the volume of data required to train the BCI algorithm; this will be higher than the sample size required to provide 80% power to detect a significant (e.g.,  $p < 0.05$ ) difference between groups in the simulated interventional study. For the binary LR techniques like that used to develop the predictive model, however, much larger sample sizes are required to provide predictive accuracy(43). Given that a range of BCI techniques are likely to be trialled and that most of the variation will be taking place in a small proportion of samples, data pertaining to a large number of specimens will be required. All eligible patients who have grown an organism in a urine specimen during the a five year period from 17th May 2017 will be recruited for the development and testing of the predictive algorithm. This period has been chosen to provide a balance between strength of model, the amount of data available, computational power required and 'concept drift' i.e., changes in susceptibility patterns and laboratory practice over time; the most recent AST practice change in LCL was implemented 17th May 2017(44). This period will provide an estimated sample size of at least 250,000 specimens, which will pertain to fewer patients than that number as some will have had urine specimens sent more than once.

### **3.1.4 Pseudonymised Data Access**

Patients do not exist solely within a single healthcare setting, but rather move through local healthcare systems according to their needs(45). The predictive value of the model will therefore theoretically be significantly improved by access to integrated data sets from across Liverpool primary and secondary care systems, to give an accurate picture of their care up to the point a urine sample is sent to the laboratory. This will be achieved using infrastructure provided by Mersey Care NHS Foundation

Trust's NHS Combined Intelligence for Population Health Action (CIPHA) programme supported by Liverpool City Region Civic Data Cooperative (CDC) and the CIPHA's Data Action Research Group (DARG), which are entities based within NHS Cheshire and Merseyside Integrated Care board (ICB) (46,47). Following relevant approvals (see section 4.2), researchers will be given access to data within the NHS ICB/CIPHA regional secure data environment (SDE) that has been pseudonymised to a level that prevents re-identification using any means reasonably likely to be used by either researchers or any other person, according to NHS Data Services for Commission Regional Offices (DSCRO) standard operating procedures (48):

- Removal of patient name and hospital number
- Replacement of NHS number with generic study number
- Replacement of specimen number with generic study number
- Replacement of locations with dummy locations and location type (e.g. medical ward, surgical ward, GP practice), removal of patient address and postcode pseudonymisation

Pseudonymisation code keys are kept within an encrypted drive within the NHS ICB/CIPHA secure data environment for 10 years from the end of the study, and are only accessible by ICB/CIPHA employees (they are not accessible by the research team).

Access to linked, pseudonymised data is the optimum approach for two reasons:

- Regional integration of hospital and community data is critical to this project. CIPHA is an entity designed with that sole purpose that has already proven itself effective in the COVID-19 pandemic(49). Its position as a link between different data controllers to generate social license for integrated data uses/intelligence is well placed to integrate hospital and community data into single pseudonymised datasets.
- LUHFT already has access to the necessary data science resource from University of Liverpool without depending on stretched Trust financial and human resource.

### **3.1.5 Data Cleaning**

Once researchers have been given access to the data, cleaning of the dataset will be required because:

- Intrinsic resistance patterns will be populated in the dataset according to European Committee on Antimicrobial Susceptibility Testing (EUCAST) rules to enable proper interpretation (for

instance, amoxicillin will not be tested on most *Klebsiella* species because of intrinsic resistance, but this will be a blank in the starting dataset, which will need to be filled in with an 'R')(50)

- Organisms susceptible at increased antimicrobial exposure 'I' can be interpreted as susceptible in the context of urinary tract infection according to EUCAST rules(51). They will therefore be reclassified as 'S' to facilitate the use of binary LR (see below).
- Resistance data from multiple organisms grown in the same specimen will be inputted in the same way as for individual growth, but organisms will remain linked by pseudonymised specimen number to facilitate trial of composite 'functional' resistance of multiple organism growth as an input (i.e., if either organism in the specimen is resistant report the specimen as 'R', if both are susceptible report as 'S').
- Some data elements (for instance specimen site) will have been recorded manually and there may therefore be typographical errors that require correction to make them statistically processable.
- Assessment of data completeness will be required and strategies for managing missing data developed.
- Other data transformations may need to occur to facilitate processability or economise on computing power, e.g., feature scaling or dimensionality reduction(52).

## 3.2 Development of an Adaptive Clinical Prediction Model

### 3.2.1 Bayesian causal inference Model Training

All data manipulation, analysis and algorithm writing will take place within the CIPHA TRE. The output of the adaptive clinical prediction model will be a quantification of the level of statistical probability of susceptibility to a specified antibiotic, as displayed in Figure 3.

## ADAPT-AST Protocol

[figure not shown]

Figure 3: Laboratory workflow and susceptibility testing are reimagined by making use of prior information and prediction algorithms. In this situation, 4 antimicrobials are selected for testing from a panel of 8 for ease of illustration, instead of the panel of 7 used in the study.

The antimicrobials for which susceptibility probability outputs will be created will be those with AST methods available which provide information about the likely activity of antimicrobials which are licensed for the treatment of UTI in the UK. These antimicrobials are listed in Table 2 according to their WHO AWaRe category.

WHO AWaRe Category	Access	Watch	Reserve	Screening
Antimicrobials	Amikacin Amoxicillin Amoxicillin-Clavulanate Cefalexin Chloramphenicol Gentamicin Trimethoprim-Sulfamethoxazole Nitrofurantoin	Ceftazidime Ciprofloxacin Ertapenem Erythromycin Fosfomycin (oral) Meropenem Piperacillin-tazobactam Teicoplanin	Aztreonam Ceftazidime-avibactam Ceftolozane-tazobactam	Cefoxitin Cefpodoxime

#### ADAPT-AST Protocol

	Pivmecillinam Trimethoprim	Temocillin Vancomycin		
--	-------------------------------	--------------------------	--	--

Table 2: The group of antimicrobials from which ADAPT-AST will select a panel of 7 to test on each urine specimen, stratified by WHO AWaRe category. Cefpodoxime and cefoxitin are also part of the classification, but they are used purely in the laboratory for resistance phenotype screening purposes in Liverpool so have been left out of category as screening antimicrobials here.

A range of different BCI techniques will need to be trialled and compared for this process using open-source R, Stan, and Python coding languages on the open-source R-studio and PyCharm proprietary integrated development software platforms. A range of different BCI techniques will need to be trialled and compared for this process. However, binary LR with Markov Chain Monte Carlo (MCMC) estimation of the posterior distribution is likely to be the most appropriate initial trial technique for this because:

- A predictive model incorporating multiple input variables needs to be developed
- A supervised BCI statistical technique can be used here because the labels of the input variables are known
- The output variable only has two possible outcomes: 'S' for susceptible and 'R' for resistant
- The output variable can be expressed as a probability of outcome 'S' or 'R'
- Parameters will need to be estimated by random sampling from a posterior probability distribution which is influenced by random variables and in which there is probabilistic dependence between samples(53,54)

Proposed models will be trained on data from a randomly selected 80% of eligible specimens from the retrospective data from between 17th May 2017 and the present. The models will be based on a consistent time frame prior to each urine specimen chosen. This is because firstly the influence of prior data on current antimicrobial susceptibility probability is likely to diminish with increasing time, and secondly it will avoid bias being introduced by more data being available for specimens at the end of the dataset(39). Different periods will be trialled for those which give the highest predictive value. Wherever possible, algorithms will be designed in a 'modular' way with intuitive exchangeable components. This will increase the potential scalability and reapplication of algorithms in other settings (e.g., LMICs) with minimal algorithm modification.

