Study Title	Adaptive Prediction of Antimicrobial Susceptibility and its Implementation to Improve the Management of Urinary Tract Infection
Internal ref. no. (or short title)	ADAPT-AST (Adaptive Antimicrobial Susceptibility Testing)

Study Design	Retrospective observational study
Study Participants	Demographic, antimicrobial prescribing and microbiology specimen data from patients >18 years in the catchment area served by Liverpool University Hospitals NHS Foundation Trust and Liverpool Community Health
Planned Size of Sample (if applicable)	> 250,000 specimens estimated (the number of patients will be fewer because some patients will have had more than one specimen sent)
Outcomes	
Primary outcome:
 
The number of antimicrobial susceptibility results that 'should' spur action by a clinician on the day that actual first-line AST results were reported (in green on Figure 5).
 
Secondary outcomes:
 
 
1. The number of days until a result that 'should' spur action by a clinician (in green on Figure 5).
 
2. The number of antimicrobial susceptibility results that 'could' spur action by a clinician on the day that actual first-line AST results were reported (in yellow on Figure 5).
 
3. The number of days until a result that 'could' spur action by a clinician (in yellow on Figure 5).
 
4. The projected health economic cost per specimen, including laboratory (e.g., consumable cost) and patient (e.g., drug toxicity, clinical failure) measures guided by the above criteria.
 

Follow up duration (if applicable)	Not applicable
Planned Study Period	3 years
Project Question/Aim(s)	
 
1. Can causal, explainable Bayesian causal inference (BCI) approaches be used to develop/(re)validate (train/test) clinical prediction models for prediction of urine organism antimicrobial susceptibility using NHS care data?
 

	2. Can the resulting ADAPT-AST adaptive, informatics-based (data-driven and system-wide) approach target AST for UTI better than existing approaches can, thereby improving timeliness of clinical decision making and saving resources through efficiency?
--	---

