- Admission/consultation/past diagnoses data: Resistant organism colonisation is more likely in patients who have been exposed to healthcare(38).
- Prescribing data: Previous antimicrobial exposure is one of the key routes to development of drug resistance through induction of organism-level molecular resistance mechanisms and population-level selection of resistant organisms. Data on non-antimicrobial drugs will also be collected as this may be a surrogate marker of contact with healthcare that influences AMR risk e.g., drugs for benign prostatic hypertrophy(39)
- Microbiology data: Previous colonisation with an antimicrobial resistant organism is a risk factor for subsequent infection with an antimicrobial resistant organism; susceptibility data for all types of patient specimen will therefore be analysed (with appropriate algorithmic weighting), not just urine specimens(40). Specimen type and location type will also provide important information about risk factors (e.g., catheter specimen of urine, urology clinic specimens).

Protected characteristics were also considered for inclusion to prevent unintentional algorithmic discrimination. Characteristics considered were those defined by UK law: pregnancy, marital status, race, sexual orientation, gender reassignment, disability, religion and nationality (41,42). Data on these characteristics will not be collected because: 1. There are no proven or plausible reasons why these characteristics should directly and significantly impact AMR risk; 2. protected characteristic data contained within the relevant systems is likely to be incomplete and unreliable; 3. some protected characteristics (e.g., race or nationality) may increase the risk of participant identification due to the rarity of some characteristic types in the Liverpool area.

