### **3.2.2 Bayesian causal inference Model Testing**

The statistical performance of models will then be assessed ‘out of sample’ on the remaining 20% of specimens in the same retrospective dataset. The techniques used to assess and refine the initial LR-derived model will be developed using R, Stan, and Python programming languages, and will consist of:

- Counterfactual analysis: Input variables will be sequentially removed from and returned to the model to ascertain their likely causative impact, and therefore determine whether they should be included in the final model(27). Where sufficient data are available, sensitivity analyses will also be performed to analyse to ensure that unjustified prediction inequalities do not occur(41).
- Scoring rule loss functions: Different performance assessments will be required depending on the models used. For LR, measures such as log loss score and AUC-ROC will provide measures of model accuracy by quantifying difference between the probability of antimicrobial susceptibility predicted by the model and observed antimicrobial susceptibility(55,56).

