## **3.3 Development and Clinical Evaluation of ADAPT-AST in a simulated clinical setting**

### **3.3.1 AST Decision Making Algorithm Development**

The final stage of the project will be evaluating the potential clinical and resource impact of the testing framework on the same 20% of samples used in the testing dataset above. To do this, a clinically suitable AST decision making model first will need to be developed. Comparison of a range of algorithmic approaches is likely to be required, but the aim of the first decision model trialled will be to select 7 antimicrobials for testing (the number in the standard first-line panel currently tested under existing LCL SOPs). The antimicrobials that will be initially eligible for AST selection are those for which probability calculations will be outputted, listed above in Table 2.

The first prioritisation approach trialled will be to rank antimicrobial choices in descending order of susceptibility uncertainty except for cefpodoxime and cefoxitin, then to apply an algorithm in Figure 4 to ensure that a mixture of oral and intravenous agents is tested.

[figure not shown]

Figure 4: Algorithm used to select 7 antimicrobials from the sorted shortlist.

\*Amoxicillin, Amoxicillin-Clavulanate, Aztreonam, Cefalexin, Ceftazidime, Phenoxycephalothin, Piperacillin-tazobactam.

Cefpodoxime or cefoxitin are not used as treatments in the local area, but resistance to either antimicrobial indicates a high probability of resistance mechanisms which preclude use of some beta lactams (BL) and beta-lactam-beta-lactamase-inhibitor combinations (BL-BLIC)(57,58). Therefore, the algorithm will also be designed for cefpodoxime and cefoxitin to only be tested when their susceptibility is sufficiently uncertain (a defined classification threshold will be calculated for this) and there is a chance of the affected BLs / BL-BLICs, cefpodoxime and cefoxitin all being tested as part of the panel of 7.

No additional weighting, ranking or exclusion criteria will initially be applied, but depending on evaluation based on a priori microbiology / clinical / health economic knowledge, measures may need to be taken to further steward the AST choices. These may include exclusion of certain antimicrobial choices which are less practically useful for UTI but for which resistance uncertainty may be high (e.g., teicoplanin) or algorithmic prioritisation/exclusion/weighting measures for factors such as WHO

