### **3.3.4 Potential Limitations of Simulated Interventional Study**

Given that the intervention in this study is simulated, there is no risk of harm to patients through incorrect testing decisions. However, the lack of intervention means that the impact on the eventual prescription cannot be assessed, because prescriber behaviour is not incorporated. Future randomised interventional studies will therefore need to be performed to assess impact before the approach could be deployed in the clinical setting. Another potential limitation is missing data, either from patients who have been transferred from outside of the region, or who have passed through areas without electronic prescribing data (e.g., Accident and Emergency, Intensive Care). Although this will be a small proportion of the antibiotics prescribed and administered, the potential impact of this will need to be considered when the model is explained. An ability to distinguish between transfer from out of area (for example, a high AMR setting) and patients presenting to healthcare for the first time may also affect the predictive value of an apparent lack of healthcare exposure for a lower AMR probability by diluting its effect. Some antimicrobial susceptibility data will also be missing due to agents not having been tested; the impact of this will need to be weighted within the process of algorithm development.

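### The 80/20 split is drawn by specimen and not by patient, so one patient's results can sit in both the training and the test set

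*Protocol*

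**What the plan says.** Section 3.2.1 fixes the training set: "Proposed models will be trained on data from a randomly selected 80% of eligible specimens". Section 3.2.2 then assesses performance "on the remaining 20% of specimens in the same retrospective dataset" and describes that as out-of-sample. Section 3.3.1 runs the simulated clinical evaluation "on the same 20% of samples used in the testing dataset above".

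Patients recur in the data. Section 3.1.3 says of the 250,000 or more specimens: "which will pertain to fewer patients than that number as some will have had urine specimens sent more than once". The study summary says the same: "the number of patients will be fewer because some patients will have had more than one specimen sent".

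Section 3.1.2 expects results within a patient to be related: "Previous colonisation with an antimicrobial resistant organism is a risk factor for subsequent infection with an antimicrobial resistant organism". For that reason, "susceptibility data for all types of patient specimen will therefore be analysed", not only urine results. Section 3.2.1 restricts each specimen's inputs to a fixed period before that specimen.

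No section groups the split by patient, limits the number of specimens per patient or holds out a later period. Section 3.1.5 links organisms within one specimen, but this does not link the specimens of one patient.

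**The concern.** A test set is out of sample only if its outcomes are independent of those used to fit the model. With repeat specimens and a split by specimen, a model can be fitted to a patient's results and then scored on another result from that patient. Some of those training results will be later than the test specimen, and these could never be known when the system is in use. A test specimen's own result can also enter the look-back inputs of a later training specimen.

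Using a patient's earlier results as inputs is intended and is not the fault. The fault is that the patient's results also serve as training outcomes.

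The 20% is the only stated evidence of out-of-sample performance, and it is also the evaluation set for the comparison with current practice. Section 3.2.1 plans to compare several techniques, and the overlap need not flatter them all equally. It also hopes to reapply the algorithms in other settings, where every patient would be new to the model.

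**Working it through.** **Inputs.** From the protocol: 80/20 random split by specimen (3.2.1, 3.2.2), and at least 250,000 specimens (3.1.3), so about 0.8 × 250,000 = 200,000 for training and 0.2 × 250,000 = 50,000 for testing. The 250,000 is an estimate of available data and cannot be reproduced by a formula. Not given: number of patients, within-patient correlation, results per agent, number of model inputs.

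**Overlap for a patient with k specimens.** This follows from the stated split, with specimens allocated independently.

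- Patient in both sets: 1 − 0.8^k − 0.2^k.
- Test specimen has another specimen of that patient in training: 1 − 0.2^(k−1).
- Test specimen has a later one in training: the mean of 1 − 0.2^j over j = 0, …, k−1, where j is the number of later specimens.

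| k | Both sets | Any other in training | A later one in training |
|---|---|---|---|
| 2 | 1 − 0.64 − 0.04 = 32% | 80% | (0 + 0.8)/2 = 40% |
| 3 | 1 − 0.512 − 0.008 = 48% | 96% | (0 + 0.8 + 0.96)/3 = 59% |
| 5 | 1 − 0.3277 − 0.0003 = 67% | 99.8% | 3.7504/5 = 75% |

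**Share of the test set affected.** This needs the distribution of k, so it is an assumption. With a geometric distribution of mean m, p = 1/m and q = 1 − p, the share is 1 − p²/(1 − 0.2q)². For m = 1.1, 1.5, 2 and 3 this gives 14%, 49%, 69% and 85% of test specimens.

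**Possible size of the optimism.** This is an illustrative simulation and every setting is assumed: intercept −1; 10 inputs with log-odds 0.3 among 30 or 90 in total; 1 + Poisson(1) specimens per patient; the patient's previous result included as an input; ridge logistic regression. The mild case has a patient SD of 1 logit and 30% of input variance at patient level; the worst case has 2 and 70%. Entries are AUC under the specimen split minus AUC under a patient split.

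| Results for the agent | Inputs | Mild | Worst | SE |
|---|---|---|---|---|
| 1,000 | 30 | 0.002 | 0.006 | 0.0015 |
| 1,000 | 90 | 0.007 | 0.032 | 0.0015 |
| 5,000 | 30 | 0.005 | 0.004 | 0.001 to 0.002 |
| 5,000 | 90 | 0.001 | 0.004 | 0.001 to 0.002 |
| 20,000 | 30 or 90 | −0.002 to 0.003 over all four settings | | 0.002 |

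An independent rerun at 1,000 results gave 0.002 to 0.008 with 30 inputs and 0.003 to 0.035 with 90, and little beyond noise at 5,000. A random forest with 30 inputs gave −0.008 (mild) and 0.020 (worst) at 1,000 results (SE 0.006), and −0.001 and 0.010 at 5,000 (SE 0.005).

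**The case against.** The strongest reply has four parts.

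1. **The effect is immaterial for the planned setting.** The likely first technique is logistic regression, on a very large dataset. The largest simulated value needs 1,000 results, 90 inputs and the worst-case patient effects together, and none of these is a document figure. At 5,000 results the mild and worst cases do not line up as the mechanism predicts, and most random forest values lie within about two standard errors of zero. All of this stands. But section 3.3.4 confirms that "Some antimicrobial susceptibility data will also be missing due to agents not having been tested", without saying how many results each agent has, so sparse agents cannot be ruled out.

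2. **Part of the overlap is realistic.** In the same catchment, a returning patient's earlier results could properly be in the training data; only later ones could not. In a further run at 1,000 results, total excesses of 0.002, 0.006, 0.009 and 0.030 had later-result components of 0.001, 0.002, 0.003 and 0.013, about half or less each time. This narrows the fault but does not remove it: later results still enter training, and performance in patients new to the model is not measured.

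3. **Sampling error is larger.** With 1,000 results there are 200 test results, and the simulated SD of the AUC was 0.041 to 0.045 under the specimen split, so even the worst-case excess is below one SD. This is true for one agent. For logistic regression at that size, however, the excess was positive in every setting, so averaging over agents would not cancel it.

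4. **Some of this belongs in an analysis plan, and section 3.3.4 requires randomised studies before deployment.** Clustering of uncertainty can indeed be left to the analysis plan. The unit of the split cannot be treated as omitted detail, because the protocol names the specimen in both places.

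**Conclusion.** The concern holds, at modest severity. The protocol fixes the specimen as the unit of the split, says patients recur, and expects their results to be related. The overlap probabilities for given k follow from the stated split alone. The share of the test set affected and the size of the optimism rest on assumptions, because the document gives none of the quantities needed to estimate them. For logistic regression on commonly tested agents the optimism is probably negligible. It could be visible, up to a few hundredths of AUC on the assumed settings, for agents with about 1,000 results and many inputs, and may be somewhat larger for more flexible techniques. The case for changing it is that the remedy is standard and nearly free.

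**What to change.** In sections 3.2.1 and 3.2.2, randomise patients to the 80% and 20% sets by pseudonymised study number (listed in Table 1 and section 3.1.4), so that all of a patient's specimens stay on one side. Overlap is then zero by construction, expected set sizes are unchanged, and a test patient's earlier results remain usable as inputs. Cluster test-set uncertainty on patient, here or in the analysis plan. A temporal hold-out could be added for the drift named in sections 1.2 and 3.1.3, with patients still kept apart; on its own it would not remove patient overlap.

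The cost is one line of text, a slightly lower reported AUC and some precision. At an assumed within-patient correlation of 0.5:

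- Exactly 2 specimens per patient: design effect 1 + 0.2 × 1 × 0.5 = 1.10 (specimen split) against 1 + 1 × 0.5 = 1.50 (patient split). √(1.50/1.10) = 1.17, so intervals are 17% wider.
- 1 + Poisson(1) specimens: E[k²]/E[k] = 5/2 = 2.5, giving 1 + 0.2 × 1.5 × 0.5 = 1.15 against 1 + 1.5 × 0.5 = 1.75. √(1.75/1.15) = 1.23, so 23% wider.

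Over correlations of 0.2 to 0.8 the range is 7% to 33%. At correlation 0.5 the effective test size becomes 50,000/1.75 = 28,571 to 50,000/1.50 = 33,333, instead of 50,000/1.15 = 43,478 to 50,000/1.10 = 45,455, which the study can absorb. For a sparse agent with 200 test results, the simulated SD of the AUC rose only from 0.041–0.045 to 0.043–0.048.
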